3.2.2 Exclusion criteria

- Subjects with severe obstructive sleep apnea (RDI ≥ 30 events/hour) or with significant O₂ desaturation $< 80\%$ during sleep that might have potential benefit from the CPAP treatment. CPAP treatment will be offered to these subjects.
- Subject with known obstructive sleep apnea and currently on CPAP treatment

Recruitment of subjects will be done at the antenatal care clinic. Screening for eligibility by investigators will be done, consecutively. Subjects who meet the inclusion criteria without any of the exclusion criteria will be approached to participate in the study.

3.3 Randomization and allocation

A randomization list will be generated and stratified by trimesters. For each stratum, a block randomization with varying block size from 4 to 8.

Preparation of randomization will be done by a third party, not involved in the clinical trial. Randomization sequence codes were generated using centralized computer system. Once eligible participants had agreed to participate the study and signed informed consent, the investigators entered clinical details into the system. Then the computer system generated the automatic randomization sequence and immediately sent back to the investigators for further allocation accordingly. After randomization and allocation, participants in the CPAP intervention group received CPAP treatment nightly throughout pregnancy until delivery.

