3. METHODOLOGY

3.1 Study design and setting

The study design will be a multicenter randomized-controlled trial in 3 tertiary care hospitals including Ramathibodi Hospital, Phramongkutklao Hospital and Rajavithi Hospital.

3.1.1 Ramathibodi Hospital is a [university hospital](#) of the Faculty of Medicine Ramathibodi Hospital which is a faculty within [Mahidol University](#) and the fourth oldest medical school in Thailand. The hospital serves at least 5,000 out-patient visits per day and in-patients with more than 1,000 beds for tertiary medical care. The hospital provides approximately 3,000 antenatal care service and delivery each year. It will be the primary site of the research investigation. The study will initiate here in June 2016 and followed by other centers. The study will take approximately 2 years for the accrual time to achieve the target number of participants and another year for the completion and analysis.

3.1.2 Phramongkutklao College of Medicine is the first and only medical cadet school in [Thailand](#). The college is the seventh medical school established in Thailand by the will of [King Bhumibhol Adulyadej](#). Phramongkutklao College of Medicine is an affiliated college of [Mahidol University](#). It is the teaching hospital accommodating 1,200-bed in the tertiary level. The hospital provides approximately 3,000 antenatal care service and delivery each year. The research will start soon after the study initiation in Ramathibodi Hospital once the ethics committee and funding are approved. The study will take approximately 2 years for the accrual time to achieve the target number of participants and another year for the completion and analysis.

3.1.3 Rajavithi Hospital is a 1,200-bed medical center accommodating 40,000 in-patients and 1,000,000 out-patients yearly or a daily average of 4,000 patients, with 200,000 referral patients (both in and out patients). The hospital provides medical service at standard health promotion in tertiary levels and above, including quality referral system. The hospital provides approximately 4,000 antenatal care service and delivery each year. The research will start soon after the study initiation in Ramathibodi Hospital once the ethics committee and funding are approved. The study will take approximately 2 years for the accrual time to achieve the target number of participants and another year for the completion and analysis.

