3.2.1 Inclusion criteria (ALL criteria)

- Singleton pregnant women age ≥ 18 years without significant medical conditions such as immunocompromised status, chronic infection (HIV infection, tuberculosis), chronic lung and cardiac conditions, chronic kidney disease, thyroid disease, or neuromuscular disease.
- Pregnant women attending the 1st antenatal care and intending to deliver at one of the study hospitals with gestational age < 16 weeks
- Thai nationality with ability to use Thai language proficiently both in spoken and written language.
- Have been diagnosed as high-risk pregnancy by obstetricians by having any of the following conditions

- a. Chronic hypertension prior to pregnancy
- b. Hypertension during pregnancy before 20week gestation.
- c. Pre-eclampsia/gestational hypertension during recent pregnancy
- d. Obesity defined by pre-pregnancy body mass index (BMI) ≥ 27.5 kg/m²
- e. Having diabetes mellitus or history of gestational diabetes in previous pregnancy
- Having SDB by either definition
 - a) RDI ≥ 5 events/hour by sleep testing at either point of testing during early pregnancy (0-16 GA week) or late pregnancy (GA 24-28 week)
 - b) OR Presence of snoring (either as frequent snoring ≥ 3 times/week or loud snoring) prior to or occurring during pregnancy
- Sign written informed consent

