3.7.2 Control Group

- Subjects will receive standard antenatal care and follow-up plan similar to the intervention group.

Primary outcome

- Systolic and diastolic blood pressure, which will be measured at rest using sphygmomanometer twice on both arms by research nurses during daytime ANC at 10:00-12:00 pm at randomization (GA 0-16 week), 1.5-2 month after randomization (GA 18-20 week), and 3-4 month after randomization (GA 24-28 week), 5-6 month after randomization (GA 32-34 week) and monthly (GA>35 week) until delivery

Secondary outcome

- 24-hour ambulatory blood pressure monitoring (daytime versus night time) using the non-invasive technique from pulse transit time (SomnoTouch NIBP).
- Pregnancy complication listed as composite endpoints below

(Composite endpoint): A combination of clinical endpoints in maternal and fetal outcomes, data from Ramathibodi hospital during 2013-2014) *

- **Composite 1:** hypertensive disorder of pregnancy;
- **Composite 2:** hypertensive disorder of pregnancy or preterm labor or fetal growth restriction
- **Composite 3:** Preterm labor or fetal growth restriction, or severe pre-eclampsia or eclampsia or death; (composite 3 incidence=10%)

*Given that the incidence of hypertensive disorder incidence= $136/3787=3.6\%$;
gestational diabetes incidence= $601/3787=15.9\%$; fetal growth restriction incidence= $157/3787=4.1\%$; preterm labor incidence=10%; and severe pre-eclampsia/eclampsia/HELLP syndrome incidence= $(43+ 1+3=46/3787=1.2\%)$, respectively.

- Individual component of the composite endpoints including incidence of hypertensive disorder of pregnancy, gestational diabetes, preterm labor, and fetal growth restriction
- Glucose level, Oral Glucose Tolerance Test (OGTT), HbA1C
- Fetal ultrasound results: uterine Doppler arterial blood flow, fetal growth restriction
- Neonatal outcome: birth-weight, APGAR score, Length of stay, NICU admission

- Placenta character: weight will be measured at birth by the neonatal nurse.

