### **3.3 Randomization and allocation**

A randomization list will be generated and stratified by collaborative center. For each stratum, a block randomization with varying block size from 4 to 8 will be performed using computerized program by STATA.

Preparation of randomization will be done by a third party, not involved in the clinical trial. The randomized code will be sealed into the sequentially numbered, opaque sealed envelopes (SNOSE) and send to each collaborative center. Investigators enrolling the patients will not be aware of the order of the randomization until opening the envelope for subject allocation.

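### In a three-hospital trial the current Protocol neither stratifies randomisation by hospital nor adjusts for hospital in the primary DBP test; the cost is precision, not bias

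*Protocol*

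**What the plan says.** Section 3.1 of the Protocol describes a "multicenter randomized-controlled trial in 3 tertiary care hospitals". Section 3.3 then states "A randomization list will be generated and stratified by trimesters", followed by "For each stratum, a block randomization with varying block size from 4 to 8". The codes come from one central computer system. No hospital stratum and no separate list per hospital is described.

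Section 3.3 of the combined protocol and SAP differs: "A randomization list will be generated and stratified by collaborative center", with sealed envelopes sent to each center. The Protocol is the later text. Its section 3.9.1 records the 2019 increase to 360 cases, and its section 3.10.4 reports that the interim analysis was not done. Its trimester rule is therefore the current one. No reason is given for dropping center.

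On timing, section 3.2.1 admits "Pregnant women attending the 1st antenatal care and intending to deliver at one of the study hospitals with gestational age < 16 weeks", and the primary outcome schedule in section 3.7.2 places the baseline reading "at randomization (GA 0-16 week), 1.5-2 month after randomization (GA 18-20 week"). Section 3.2.1 also lets sleep-disordered breathing be shown by a test at 24 to 28 weeks.

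In section 3.10.4 the primary test is a two-sided t-test on change in DBP, with no covariates. Composites are compared by chi-square or Fisher's exact test. The logistic models adjust for covariates that are not named.

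**The concern.** Hospital is a natural source of between-woman variation here. Obstetric care is presumably local, the primary blood pressure is a manual reading by research nurses at antenatal visits, and the hospitals start one after another. A multicentre trial usually handles such a factor by stratifying on it, adjusting for it, or both. The current Protocol does neither.

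The factor it does use has little left to separate. Under 16 weeks covers the first trimester and the first weeks of the second.

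At stake are avoidable noise in a comparison designed around 2.5 mmHg and, in an open-label trial, an argument over the result if the arms turn out visibly unequal in one hospital.

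**Working it through.** **Inputs from the Protocol.** Section 3.9.1: SD 7.4 mmHg, difference 2.5 mmHg, two-sided alpha 0.05, power 0.80, 139 per arm before loss, 334 in total (167 per arm) after loss. Section 3.1: three hospitals. Section 3.3: blocks of 4 to 8.

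**Assumptions not in the documents.** The recruitment split between hospitals, the share of women entering in the first trimester, the hospital gap in DBP change, and the between-hospital SD.

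**The plan's own figure.** n per arm = 2 × (1.960 + 0.842)² × 7.4² / 2.5² = 137.5, so 138 by the normal approximation and 139 by the t-test. The stated 139 reproduces. It does not depend on the stratification factor.

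**Chance imbalance within one hospital.** With arm totals close to equal, the SD of the arm difference among n women in one hospital out of N is √(n(1 − n/N)).
- For n = 60, N = 334: √(60 × (1 − 60/334)) = 7.02, and 1.96 × 7.02 = 13.8 women.
- The shift in the treatment estimate is gap × 13.8/167. A gap of 3 mmHg gives 0.25 mmHg and a gap of 5 gives 0.41, which is 10% to 16% of 2.5.
- At one SD the shift is 3 × 7.02/167 = 0.13 to 5 × 7.02/167 = 0.21 mmHg.

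**Simulation check.** Permuted blocks of 4, 6 and 8, N = 334, 80% first-trimester entry, recruitment split 3:3:4 or 80:10:10, 2,000 runs per scenario, gaps of 2 to 5 mmHg at one hospital:

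| Stratified by | Mean absolute arm difference per hospital | 95th percentile | 95th percentile of absolute shift |
|---|---|---|---|
| Trimester only | about 4 to 7 | 10 to 17 | 0.12 to 0.50 mmHg |
| Hospital | 0.8 | 2 | 0.02 to 0.06 mmHg |

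**Power, and where the gain comes from.** Take 139 per arm and let s be the between-hospital SD contained in the total of 7.4. The residual SD is √(7.4² − s²), and SE = SD × √(2/139).
- Without hospital: SE = 0.888 and power = Φ(2.5/0.888 − 1.96) = 0.804.
- Stratum plus hospital term: SE = 0.880, 0.855, 0.811 for s = 1, 2, 3.
- Stratum with the plain t-test: the estimate varies with the smaller SE but is judged against 1.96 × 0.888, so power = Φ((2.5 − 1.740)/SE).
- Hospital term without the stratum: SE is multiplied by about √(1 + 2/278), for two extra parameters.

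| s (mmHg) | Neither | Stratum, plain t-test | Hospital term, no stratum | Both |
|---|---|---|---|---|
| 1 | 0.804 | 0.806 | 0.808 | 0.811 |
| 2 | 0.804 | 0.813 | 0.830 | 0.833 |
| 3 | 0.804 | 0.826 | 0.866 | 0.869 |

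Once hospital is in the model, the stratum adds about 0.003.

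**The case against.** The case against is substantial, and much of it stands.

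- **Validity.** Trimester-stratified randomisation balances hospitals in expectation. Type I error and expected bias are unaffected, and chance imbalance is already reflected in the t-test's standard error. This stands.
- **Change scores.** A constant difference between hospitals or nurses in how pressure is read cancels in the change from baseline. Only hospital differences in change over time, or drift, carry through. This stands, so the manual reading is weak support by itself.
- **Calendar time.** Small central blocks keep the arms close to equal over time. While only the first hospital recruits, the same blocks balance its women. Staggered starts therefore reduce within-hospital imbalance. This stands, and the simulation, which mixes hospitals at random, does not credit it.
- **Feasibility.** The Protocol reads partly as an account of what was done. Section 3.12 has enrollment ending in October 2019, so changing the randomisation system may no longer be possible. This stands and moves the weight to the analysis.
- **Assumed sizes.** The 3 to 5 mmHg gap exceeds the treatment effect sought and has no source in the documents. The quoted shifts are 95% limits. This stands.
- **Later entry.** The 24 to 28 week sleep-test route leaves open whether some women were randomised later, in which case trimester would separate more. The documents do not settle this.

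None of this supplies a hospital term in the analysis or explains why the center stratum was dropped.

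**Conclusion.** The point holds as a matter of precision and robustness. In a three-hospital trial, hospital is neither restricted at randomisation nor included in the primary analysis, and the stratum that replaced it separates little if all entry is under 16 weeks.

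The size is modest. Under the assumptions above, the shift is up to about 0.25 to 0.41 mmHg for a hospital of 60 women, and power goes from 0.80 to between 0.81 and 0.87 depending on the assumed hospital SD. If hospitals do not differ in DBP change, the gain is essentially nil.

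A reader might infer three stronger things that the documents do not support:
- that the comparison is biased, or that nothing balances the hospitals: randomisation does so on average, and the central blocks help over time;
- that restoring the center stratum alone would deliver the power gain: with the plain t-test it gives about 0.826 against 0.869 at a hospital SD of 3;
- that trimester is an empty stratum: it still separates two groups under 16 weeks, and the late sleep-test route is unresolved.

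The change is worth making because it is specific and cheap. The trial does not fail without it.

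**What to change.** 1. In section 3.10.4 of the Protocol, add hospital as a fixed effect to the primary DBP comparison, for example a linear model of change in DBP on arm and hospital. Name hospital as a covariate in the logistic models for the composites. If the analysis has already been run, report the hospital-adjusted result beside it and label it as added later.
2. For any woman still to be randomised, stratify in the central system by collaborative center and trimester, keeping the varying blocks of 4 to 8.
3. Reconcile section 3.3 of the two documents by stating which stratum was actually used, and for which women if it changed during the trial.
4. Reconcile the 24 to 28 week sleep-test route in section 3.2.1 with the entry rule of under 16 weeks and the baseline timing in section 3.7.2, so that the content of the trimester strata is clear.

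Cost: two degrees of freedom, a few sentences, and, if randomisation is still open, one setting in the system, a few more incomplete blocks and slightly more predictability within a hospital, which the varying block size limits.

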3.4 Blinding

This is an open-label randomized controlled trial, in which subjects will know each intervention she has received between CPAP machine and standard usual antenatal care. A blinded evaluation is planned to assess the observed primary and secondary end points by a separate outcome assessor.

3.5 Variable & measurement

3.5.1 Polysomnography (PSG)

Screening for sleep disordered breathing (SDB) or obstructive sleep apnea (OSA) with either in-laboratory or home PSG will be performed depending on subject's preference. Performance of polysomnography will be done with SomnoTouchResp, which consisted of

- channels of electroencephalographies (EEG: F4M1, C4M1, O2M1)
- channels of electro-oculographies (EOG: ROC, LOC)
- Chin electromyography (EMG)
- Respiratory signals include nasal pressure transducer, oronasal thermistor, and pulse oximeter

- respiratory efforts using thoracic and abdominal respiratory inductance plethysmography (RIP)
- Sleep staging and respiratory scoring are according to the American Academy of Sleep Medicine 2012 version 2.2 [18]

1). Apnea is defined as a reduction of thermistor signal at least 90% from baseline lasting for at least 10 seconds. Obstructive apnea is classified by the presence of RIP effort, and central apnea is classified by the absence of RIP effort.

2). Hypopnea is defined as a reduction in nasal pressure transducer signal at least 30% from baseline that is associated with either O₂ desaturation $\geq 3\%$ from baseline or EEG arousal.

Apnea-hypopnea index is calculated as numbers of respiratory events per hour of total sleep time or recorded time.

3). Respiratory effort related arousal (RERA) is defined as a sequence of breaths lasting ≥ 10 seconds characterized by increasing respiratory effort or by flattening of the inspiratory portion of the nasal pressure leading to arousal from sleep that does not meet the criteria for apnea or hypopnea.

4). Additional scoring of airflow limitation and snoring time will be included as previously described [33].

Tabulation of respiratory index into apnea-hypopnea index [AHI] = no. of apnea+hypopnea/Total sleep time (hr)] and respiratory disturbance index [RDI =no. of apnea+hypopnea+RERA/Total sleep time (hr)] will be done.

3.5.2 Measurement of blood pressure

- Measurement of blood pressure using manual sphygmomanometer during ANC visit will be done twice by research nurse in sitting resting position on both arms at least 15 minutes apart. Mean of the 4 values will used for the analysis.
- 24-hour blood pressure monitoring (ABPM) will be done
 - 24-hour BP monitoring device during daytime and night-time [34, 35] had been used in pregnancy population and showed good correlation with uterine artery Doppler ultrasound. “Non-dipping pattern” on the 24- hour blood pressure monitoring had been shown can be to associated with preeclampsia and small for gestational age [36-39]. Validation of particular ABPM device is required based on the criteria set by the European Society of Hypertension position paper on ambulatory blood pressure monitoring [35]. The 24-hour BP monitoring in early pregnancy (GA<14 weeks) has been shown to predict occurrence of preeclampsia [40]. Furthermore, 24-hour SBP (per 10 mmHg [odd ratio (OR): 1.74; 95%CI:1.28-2.38; p<0.001]) was more closely associated with small-for-gestational age (SGA) than clinic BP (OR 1.40;95%CI:0.92-2.13; p=0.11) [41].
 - Non-invasive blood pressure monitoring using the calculation from pulse transit time method (PTT). Validation of this device according to the European Society of Hypertension criteria had been done in non-pregnant population [42]. The device-observer disagreement was -0.44 6.1 mmHg for SBP and -0.33 3.4 mmHg for DBP. A strong correlation was observed between Somnotouch-NIBP and auscultatory method for SBP (r=0.973) and

for DBP ($r=0.976$). The BP discrepancies did not vary according to sex ($p>0.15$), age, body weight, arm circumference ($p>0.10$). But a significant correlation was found between SBP discrepancy and height ($r=0.4$) [42].

3.5.3 Fetal ultrasound and Doppler ultrasound.

Fetal ultrasound and Doppler ultrasound will be performed by experienced obstetrician to monitor parameters listed below [43]:

- Fetal growth by ultrasound: constant (above, below, or on curve); Falling off with increasing gestation (12 week, 18-20 week, 28 week, 36 week)
- Fetal hemodynamic including uterine, umbilical, and fetal middle cerebral artery blood flow indices at mid gestation (16-25 weeks) including 1) notching (yes/no): bilateral (yes/no); unilateral (yes/no); 2) pulsatility index (PI) and resistance index (RI). PI had been shown to be predictors of preeclampsia and intra-uterine fetal growth restriction [44, 45]. However, administration of methyl-dopa to lower blood pressure in preeclampsia showed no significant change after treatment [46-48].
- Amount of amniotic fluid.

3.5.4 Measurement of plasma glucose as described by 75-g OGTT. HbA1C, fasting plasma glucose, 1-hour plasma glucose, 2-hour plasma glucose had been shown to be predictor of preeclampsia with odd ratio of 1.42 (1.33-1.52), 1.46(1.37-1.55), 1.40(1.32-1.50), 1.37(1.29-1.46), respectively [49].

3.6 Data collection

3.6.1 General management protocol for high risk women consisted of

3.6.1.1 During 1st trimester (First ANC, and subsequent 6-8 weeks ANC follow ups)

- Clinical data collection such as demographic data, underlying disease, number of gestations, last menstrual period, height, pre-pregnancy weight, pregnancy weight, neck circumference, general physical examination, and systolic and diastolic blood pressure.
- Laboratory including fasting HbA1C, fasting blood sugar, complete blood count, serologic blood test (rubella titer, anti-HIV, VDRL, Rh blood group),
- Fetal ultrasound, uterine artery Doppler

3.6.1.2 Second trimester

- Routine ultrasound at 18-20week gestation
- OGTT screening for GDM at 24-28week gestation
- 24-28week gestation: optional ultrasound depending on obstetrician's clinical decision
- Repeat blood test including fasting HbA1C, fasting blood sugar, complete blood count, and serologic blood test (anti-HIV, VDRL, Rh blood group)
- Urinary analysis

3.6.1.3 Third trimester

- Bi-weekly to weekly ANC follow-ups until delivery
- Ultrasound at 32-34week gestational age

3.7 STUDY INTERVENTION

3.7.1 CPAP intervention

- Immediately after allocation, subjects in the intervention arm will receive CPAP treatment throughout pregnancy.
- Auto CPAP machine will be prescribed to subjects with pressure in the range of 4-15 cmH₂O. Optimal pressure to eliminate respiratory events will be achieved based on the 90-95 percentile pressure.
- After determination with auto-CPAP, the machine with optimal pressure (range 4-15 cmH₂O) adjustment will be prescribed. Subjects will be encouraged to use CPAP every night, continuously. Daily record of applying CPAP will be provided with SD card within the machine, which including the start and stop time start in CPAP usage.
- During subsequent trimester when reaching 24-28 weeks of gestation, another adjustment for optimal CPAP pressure will be determined with the auto-CPAP machine. In case if higher CPAP pressure is required, adjustment will be made accordingly.
- Data of CPAP usage and adherence will be automatically recorded in the machine and available for download during follow-up.

